8.3.3.2. Osimertinib

Dose modifications for osimertinib for adverse reactions are to be made according to Table 8-2.

If a patient experiences a Grade 3 (CTCAE) or higher and/or unacceptable toxicity (any grade), where the investigator considers the AE of concern to be specifically associated with osimertinib (and not attributable to the disease or disease-related processes for which the patient is being treated), dosing will be interrupted and supportive therapy administered as required in accordance with local practice/guidelines.

If a toxicity resolves or reverts to \leq Grade 2 (CTCAE) within 3 weeks of onset, treatment with osimertinib may be restarted at the same dose or a lower dose using the rules below for dose modifications (Table 8-2) and with discussion and agreement with the sponsor's study team physician as needed. There will be no individual modifications to dosing schedule in response to toxicity, only potential dose reduction or dose interruption.

If the toxicity does not resolve to \leq Grade 2 (CTCAE) after 3 weeks, then osimertinib therapy shall be permanently discontinued and the patient shall be observed until resolution or stabilization of the toxicity.

Patients experiencing any of the following AEs will not be permitted to restart osimertinib treatment:

- Corneal ulceration
- Interstitial lung disease (ILD)
- QTc interval prolongation with signs/symptoms of serious arrhythmia
- Symptomatic congestive heart failure or asymptomatic left ventricular dysfunction that persists ≥ 4 weeks
- Liver function test abnormalities meeting Hy's Law criteria (AST or ALT \geq 3 × ULN and total bilirubin \geq 2 × ULN). All study drugs must be permanently discontinued in any patient meeting Hy's Law criteria.

Table 8-2 Recommended Dose Modifications for Osimertinib-Related Adverse Reactions

Target Organ	Adverse Reaction ^a	Dose Modification
Pulmonary	Interstitial lung disease/ pneumonitis	Permanently discontinue osimertinib
Cardiac	QTc interval > 500 msec on at least	Withhold osimertinib until QTc interval is
	2 separate ECGs	< 481 msec or recovery to baseline, then resume
		at 40 mg dose
	QTc interval prolongation with	Permanently discontinue osimertinib
	signs/symptoms of life-threatening	
	arrhythmia	
	Symptomatic congestive heart failure	Permanently discontinue osimertinib
	or asymptomatic left ventricular	
	dysfunction that persists ≥ 4 weeks	
Other	≥ Grade 3 adverse reaction	Withhold osimertinib for up to 3 weeks
	If improvement to Grade 0 to 2 within	Resume at 80 or 40 mg daily (investigator's
	3 weeks	discretion)
	If no improvement within 3 weeks	Permanently discontinue osimertinib

ECG = electrocardiogram; QTc = QT interval corrected for heart rate

Source: Table copied from Table 1 of the osimertinib package insert (see Appendix 2)

In the event that the patient experiences a drug-related hematologic toxicity, which may be related to G1T38 or osimertinib, the investigator shall dose-reduce G1T38 first (refer to Section 8.3.3.1).

In the event that the patient receiving G1T38 + osimertinib experiences an osimertinib-related toxicity requiring permanent discontinuation of osimertinib, the patient may continue G1T38 monotherapy at the discretion of the investigator.

a Adverse reactions graded by the National Cancer Institute Common Terminology Criteria for Adverse Events, Version 4.03.

Details regarding the management of specific AEs related to osimertinib are discussed in Sections 8.3.3.2.1 to 8.3.3.2.6.

8.3.3.2.1. Interstitial Lung Disease/Pneumonitis-like Toxicity

If new or worsening pulmonary symptoms (eg, dyspnea) or radiological abnormality suggestive of ILD is observed, an interruption in osimertinib dosing is recommended, and the sponsor study team shall be informed. It is strongly recommended to perform a full diagnostic workup (including high-resolution computed tomography [HRCT], blood and sputum culture, hematological parameters) to exclude alternative causes such as lymphangitic carcinomatosis, infection, allergy, cardiogenic edema, or pulmonary hemorrhage. In the presence of confirmatory HRCT scans where other causes of respiratory symptoms have been excluded, a diagnosis of ILD shall be considered and osimertinib treatment permanently discontinued.

In the absence of a diagnosis of ILD, osimertinib may be restarted following consultation with the sponsor's study team physician.

8.3.3.2.2. QTc Prolongation

Patients with QTcF prolongation to > 500 msec shall have study treatment interrupted and regular ECGs performed until resolution to < 481 msec, and then restarted at a reduced dose of osimertinib 40 mg. If the toxicity does not resolve to < 481 msec within 21 days, the patient will be permanently withdrawn from osimertinib treatment.

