4.5. Risk/Benefit Assessment

The safety profile of G1T38 observed to date in the ongoing Phase 1/2 study is similar to other CDK4/6 inhibitors such as palbociclib, with neutropenia being the most common drug-related AE and with Grade 1 and 2 gastrointestinal effects (nausea, vomiting, and diarrhea) also being observed. There have been no observed G1T38-related pulmonary, cardiac, skin, or clinically significant ophthalmic AEs to date (see Section 4.3.1).

The most common osimertinib-related AEs (≥ 20%) are diarrhea (41%), rash (34%), dry skin (23%), nail toxicity (22%), and fatigue (22%) (Tagrisso Prescribing Information 2017). Significantly less frequent, but potentially more severe osimertinib-related AEs include pneumonitis/interstitial lung disease, QTc prolongation, cardiomyopathy, and keratitis. Based on extensive nonclinical data and clinical data to date with G1T38, none of these more severe osimertinib-related AEs have been observed with G1T38 to date. This study includes appropriate exclusion criteria, baseline examinations, and on-study monitoring to carefully exclude at-risk patients and to evaluate patients for the development of these more severe osimertinib-related AEs during the course of the study. Management of osimertinib related toxicities shall follow the prescribing information for osimertinib (Tagrisso Prescribing Information 2017; see Appendix 2).

Neutropenia, the vast majority Grade 1 or 2, has also been observed with osimertinib therapy, with up to 2.2% of patients experiencing Grade 3 neutropenia. Absolute neutrophil counts will be monitored weekly for the first 8 weeks (2 cycles) then every other week for the next 2 cycles. Beginning with Cycle 5 Day 1, patients with stable ≤ Grade 2 hematologic parameters may have hematology monitored monthly (Day 1 of each cycle); patients that do not meet this criteria will continue to have every other week assessment of hematologic parameters. The neutropenia induced by CDK4/6 inhibitors, including G1T38, is reversible with interruption of therapy and dose reduction if necessary. Specific guidelines for managing neutropenia are included in Section 8.3.3.

Patients will be carefully monitored for potential gastrointestinal AEs and managed symptomatically with appropriate therapies. G1T38 will also be dosed with food as this was shown to improve gastrointestinal tolerability in the FIH study.

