8.3.3.2.4. Changes in Cardiac Contractility

Across clinical trials, LVEF decreases of $\geq 10\%$ and a drop to < 50% occurred in 4.0% (26/655) of patients treated with osimertinib who had baseline and at least 1 follow-up LVEF assessment. Based on the available clinical trial data, a causal relationship between effects on changes in cardiac contractility and osimertinib has not been established. In patients with symptomatic congestive heart failure or asymptomatic left ventricular dysfunction that persists ≥ 4 weeks, permanently discontinue osimertinib therapy (Table 8-2).

Permanent Discontinuation Due to Toxicity

Patients experiencing corneal ulceration, ILD, symptomatic congestive heart failure or asymptomatic left ventricular dysfunction that persists ≥ 4 weeks, or QTc prolongation with signs/symptoms of serious arrhythmia will not be permitted to restart osimertinib treatment. Any patient with liver function test abnormalities meeting Hy's Law criteria (AST or ALT $\geq 3 \times \text{ULN}$) and total bilirubin $\geq 2 \times \text{ULN}$) must have all study drugs permanently discontinued.

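### Table 8-2 and the protocol text set different osimertinib rules for QTc prolongation, and neither is said to govern

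*Protocol*

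**What the plan says.** Section 8.3.3.2 of the protocol opens with: "Dose modifications for osimertinib for adverse reactions are to be made according to Table 8-2". The table is headed as recommended modifications and is sourced to the osimertinib package insert. Two of its rows concern QTc:

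- **Hold.** The trigger is "QTc interval > 500 msec on at least" two separate ECGs. Osimertinib is withheld until QTc is "< 481 msec or recovery to baseline, then resume" at 40 mg.
- **Permanent stop.** The trigger is QTc prolongation with "signs/symptoms of life-threatening" arrhythmia.

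Section 8.3.3.2.2 states: "Patients with QTcF prolongation to > 500 msec shall have study treatment interrupted and regular ECGs performed until resolution to < 481 msec". Osimertinib is then restarted at 40 mg, or withdrawn for good if the level is not reached within 21 days.

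The list in Section 8.3.3.2 of events after which osimertinib may not be restarted includes "QTc interval prolongation with signs/symptoms of serious arrhythmia". The paragraph on permanent discontinuation in Section 8.3.3.2.4 repeats this: patients with "QTc prolongation with signs/symptoms of serious arrhythmia will not be permitted to restart osimertinib treatment".

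Below the table, the protocol sends the reader to Sections 8.3.3.2.1 to 8.3.3.2.6 for detail on specific events, without saying which text prevails. Section 4.5 adds that osimertinib "related toxicities shall follow the prescribing information for osimertinib".

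**The concern.** An investigator who follows the protocol faithfully can reach two answers for the same patient, on two questions: whether one reading above 500 msec requires a hold, and whether osimertinib may be given again after an arrhythmia that is serious but not life-threatening. Section 4.5 lists QTc prolongation among the less frequent but potentially more severe osimertinib reactions, so the rule ought to have one reading. At stake is consistent handling of individual patients across sites. No estimate, test or sample size depends on it.

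**Working it through.** **1. The rules side by side.** The protocol states no figure to reproduce here; this is mainly a comparison of wording.

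| Element | Table 8-2 | Protocol text |
|---|---|---|
| Measure | QTc, formula not named | QTcF (8.3.3.2.2) |
| ECGs above 500 msec needed | At least 2, separate | No number given (8.3.3.2.2) |
| What is held | Osimertinib | Study treatment (8.3.3.2.2) |
| Restart level | Below 481 msec, or back to baseline | Below 481 msec (8.3.3.2.2) |
| Time limit | None in the QTc row | 21 days (8.3.3.2.2) |
| Arrhythmia that rules out restart | Life-threatening | Serious (list in 8.3.3.2; 8.3.3.2.4) |

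**2. Two patients who separate the rules.**

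- *One reading above 500 msec.* Section 8.3.3.2.2 as worded interrupts treatment and later resumes osimertinib at 40 mg. Table 8-2 alone triggers nothing.
- *QTc above 500 msec on two ECGs, with a serious but not life-threatening arrhythmia.* Table 8-2 read alone lets osimertinib resume at 40 mg. The list above it and Section 8.3.3.2.4 forbid restart.

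**3. Differences that carry little weight.** Exclusion criterion 13a removes patients with a mean screening QTc above 470 msec, and 481 − 470 = 11 msec. For a screening baseline, recovery to baseline therefore adds nothing to the 481 msec condition (13a uses the machine-derived QTc and names no formula). The 21-day limit largely repeats the general three-week rule in Section 8.3.3.2.

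**4. How often the ECG count could matter.** Section 10.6.5 takes three tracings within about 5 minutes, so discordant tracings are possible at each ECG time point. The documents give no tracing variability. I assume a tracing SD of 5, 10 or 15 msec and a correlation ρ of 0, 0.5 or 0.8 within a triplicate. Each tracing is the true value plus a shared error (variance ρ·SD²) and its own error (variance (1 − ρ)·SD²). Given the shared error, let p be the chance that a tracing exceeds 500 msec. Averaging over the shared error:

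- any 1 of 3 = 1 − E[(1 − p)³]
- at least 2 of 3 = E[3p²(1 − p) + p³]

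Example at true QTcF 490 msec, SD 15, ρ = 0: p = P(Z > 10/15) = 0.2525. Any 1 of 3 is 1 − 0.7475³ = 58.2%. At least 2 of 3 is 3 × 0.2525² × 0.7475 + 0.2525³ = 15.9%.

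Chance of a hold at one time point (ρ = 0 / 0.5 / 0.8):

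| True QTcF | SD | Any 1 of 3 | At least 2 of 3 |
|---|---|---|---|
| 490 | 5 | 6.7 / 5.7 / 4.5% | 0.2 / 0.9 / 1.7% |
| 490 | 10 | 40.4 / 32.2 / 25.7% | 6.8 / 12.0 / 14.5% |
| 490 | 15 | 58.2 / 46.6 / 38.1% | 15.9 / 21.7 / 24.0% |
| 510 | 5 | 100.0 / 99.9 / 99.4% | 99.8 / 99.1 / 98.3% |
| 510 | 10 | 99.6 / 96.6 / 92.6% | 93.2 / 88.0 / 85.5% |
| 510 | 15 | 98.4 / 92.5 / 86.3% | 84.1 / 78.3 / 76.0% |

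The last column assumes that tracings of one triplicate count as separate ECGs, which the protocol does not say. The two triggers are close at SD 5. At SD 15 and ρ = 0 they differ by 58.2 − 15.9 = 42.3 points at 490 msec and 98.4 − 84.1 = 14.3 points at 510 msec. The stricter trigger misses less and holds more patients whose true value is below 500 msec.

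**The case against.** The best defence is that the texts can be read together. The table is only recommended and copies a label, and the protocol then points to the subsections for detail, where Section 8.3.3.2.2 uses mandatory wording. The restart list stands directly above the table and adds bars that the table lacks (corneal ulceration, Hy's Law), so it looks like a study-specific supplement. A broad prohibition and a narrow one can both be obeyed. Section 8.3.3.2 also lets the investigator interrupt osimertinib for unacceptable toxicity of any grade.

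Much of this stands. The restart conflict exists only if the table is read without the list above it. A reader might infer that the protocol permits rechallenge after a serious arrhythmia; taken as a whole, it does not. The defence fails on the hold trigger. Section 8.3.3.2 makes the table operative, no precedence is stated, and detail that drops the table's two-ECG condition does more than elaborate. Section 4.5 does not settle it either, since the protocol already departs from the copied table.

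Any 1 of 3 is also the widest reading of Section 8.3.3.2.2. Exclusion criterion 13a and SAP Section 4.2.5 work with the mean of the tracings, and the sponsor may have intended that here, but Section 8.3.3.2.2 does not say so.

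A reader might further infer that the table's unqualified QTc admits Bazett correction for holds. No section directs that: Section 8.3.3.2.2 names QTcF, and SAP Section 4.2.5 derives both corrections for reporting.

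**Conclusion.** The inconsistency is real and should be corrected, but it is minor. The differing ECG count rests on the wording alone. The arrhythmia difference is a drafting fault in the table's row, already covered by the stricter list. Reach is Part 1 only, at most 36 patients, because SAP Section 1 says that Part 2 will not be conducted. No dose-limiting-toxicity rule and no SAP analysis changes.

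The hold percentages rest on assumed variability. They show only that the trigger can matter near 500 msec, and they do not show that either trigger is the right one. A reader might infer that a two-ECG rule with a same-day repeat triplicate would lose almost no sensitivity. That depends on the repeat being independent of the first triplicate, on which the documents are silent. Such a rule, or a triplicate-mean trigger, is therefore a choice for the sponsor and not a required correction.

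**What to change.** Keep Table 8-2 as the package-insert copy and add one footnote to its QTc rows:

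> In this study QTc means QTcF. Where this table differs from Section 8.3.3.2.2 or from the list of events that bar restart, the stricter text governs: QTcF above 500 msec interrupts study treatment, with no second ECG required; restart requires QTcF below 481 msec within 21 days; and QTc prolongation with signs or symptoms of serious arrhythmia bars restart of osimertinib.

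Leave the reference to study treatment in Section 8.3.3.2.2 unchanged. Narrowing it to osimertinib would drop the hold on G1T38. In Part 1, ECGs are taken 2 and 6 hours after G1T38 alone on Cycle 1 Day -16, before osimertinib starts on Day -14, so an osimertinib-only rule would hold nothing that day.

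The cost is a short amendment, which Section 14.6 sends to the ethics committee or review board even if nonsubstantial, plus an occasional hold with restart at 40 mg after one discordant tracing. The SAP needs no change. The benefit is limited to patients still on treatment, a number the documents do not give, and to any reuse of this text.

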8.3.3.2.3. Keratitis

Keratitis was reported in 0.7% (n = 6) of the 833 patients treated with osimertinib in the AURA studies. Patients presenting with signs and symptoms suggestive of keratitis such as acute or worsening: eye inflammation, lacrimation, light sensitivity, blurred vision, eye pain, and/or red eye shall be referred promptly to an ophthalmology specialist.

8.3.3.2.4. Changes in Cardiac Contractility

Across clinical trials, LVEF decreases of $\geq 10\%$ and a drop to < 50% occurred in 4.0% (26/655) of patients treated with osimertinib who had baseline and at least 1 follow-up LVEF assessment. Based on the available clinical trial data, a causal relationship between effects on changes in cardiac contractility and osimertinib has not been established. In patients with symptomatic congestive heart failure or asymptomatic left ventricular dysfunction that persists ≥ 4 weeks, permanently discontinue osimertinib therapy (Table 8-2).

Permanent Discontinuation Due to Toxicity

Patients experiencing corneal ulceration, ILD, symptomatic congestive heart failure or asymptomatic left ventricular dysfunction that persists ≥ 4 weeks, or QTc prolongation with signs/symptoms of serious arrhythmia will not be permitted to restart osimertinib treatment. Any patient with liver function test abnormalities meeting Hy's Law criteria (AST or ALT $\geq 3 \times \text{ULN}$) and total bilirubin $\geq 2 \times \text{ULN}$) must have all study drugs permanently discontinued.

8.3.3.2.5. Skin Reactions

Changes in the CTCAE grade of skin reactions will be collected in the AE eCRF.

Photographs of skin reactions may be collected and these photographs shall be available for central review by the sponsor or designee and for external expert dermatological review if required, if patient consent is obtained.

Skin biopsies may be taken of skin reactions.

8.3.3.2.6. Diarrhea

In the event that the patient experiences drug-related diarrhea, which may be related to G1T38 or osimertinib, the investigator shall dose-reduce G1T38 first (refer to Section 8.3.3.1).

Changes in CTCAE grade of diarrhea will be captured in the AE eCRF.

8.4. Randomization and Blinding

Parts 1 and 2 are open label. In Part 1, no treatment randomization will be required. In Part 2, patients will be randomized (1:1) to receive osimertinib or G1T38 (at the RP2D) + osimertinib. Study drug administration shall begin no more than 96 hours after randomization. Randomization will be stratified according to 2 factors: the presence or absence of CNS metastases at screening and Asian versus non-Asian ethnicity.

8.5. Prior and Concomitant Medications and Procedures

All concomitant medications including prescription medications, over-the-counter preparations, herbal remedies, traditional remedies, growth factors, blood products, and parenteral nutrition taken during the 14 days prior to signing the ICF, during the study treatment, and through the Post-Treatment visit shall be documented in the eCRF.

Administration of concomitant, nonprotocol anticancer therapies prior to disease progression is not permitted during the treatment phase of this study. Concomitant radiotherapy and surgeries may be permitted as described in Section 8.8.

Administration of other concomitant investigational agents for any indication is not permitted during the treatment phase of this study.

Medications will be coded by the sponsor or designee using the most recent World Health Organization (WHO) Drug Dictionary version.

If medically feasible, patients taking regular medication(s), with the exception of prohibited medications (see below), should be maintained on those medications throughout the study period.

Refer to Appendix 4 for additional details regarding concomitant medications.

8.5.1. CYP3A4 Substrates

G1T38 has the potential to inhibit CYP3A4/5 in both a competitive and time-dependent manner based on in vitro studies. Using the FDA recommended model-based predictions in

the guidance for drug interaction studies (*US Department of Health and Human Services*, Food and Drug Administration, Center for Drug Evaluation and Research, 2012), G1T38 has the potential to significantly inhibit CYP3A4 in the gut and thus may have a clinically significant effect on orally administered CYP3A4 substrates with a narrow therapeutic index and such drugs are prohibited during participation in this study (beginning 14 days prior to first dose of study drug until 14 days after last dose of study drug).

- Prohibited, orally administered CYP3A substrates with a narrow therapeutic index, including but not limited to the following:
 - o Astemizole, cisapride, cyclosporine, dihydroergotamine, ergotamine, everolimus, pimozide, quinidine, sirolimus, and tacrolimus
- Caution should be used with concurrent use of other orally administered CYP3A substrate drugs with consideration of dose reduction of the substrate if clinical signs and symptoms of toxicity emerge (eg, muscle aches with 3-hydroxy-3-methylglutaryl coenzyme A reductase inhibitors).

The model-based calculation for inhibition of CYP3A4 in the liver predicts a marginal inhibitory effect by G1T38 and therefore the likelihood of a clinically significant drug interaction for CYP3A substrates administered via routes other than oral (eg, intravenous, transdermal, inhalation, etc.) is low.

• Caution should be used with concurrent use of non-orally administered CYP3A substrates with a narrow therapeutic index with consideration of dose reduction of the substrate if clinical signs and symptoms of toxicity emerge (eg, increased somnolence with transdermal fentanyl or intravenous midazolam).

8.5.2. **CYP3A4 Inhibitors and Inducers**

G1T38 is a substrate for CYP3A4, although the extent of metabolism by CYP3A4 is expected to be low in humans since the in vitro clearance of G1T38 in human liver microsomes and hepatocytes was low. G1T38 exposure may be altered by concomitant use of drugs, herbal supplements, or foods that are strong CYP3A inhibitors or inducers and such drugs are prohibited during participation in this study (beginning 14 days prior to first dose of study drug until 14 days after last dose of study drug).

- **Prohibited, strong inhibitors of CYP3A4**, including but not limited to the following: clarithromycin, itraconazole, ketoconazole, nefazodone, erythromycin, grapefruit juice, telithromycin, diltiazem, verapamil, and ritonavir
- **Prohibited, strong or moderate CYP3A inducers**, including but not limited to the following: phenytoin, rifampin, carbamazepine, St John's Wort, phenobarbital, bosentan, modafinil, and nafcillin

In addition, coadministration of osimertinib with a strong CYP3A4 inducer decreased the exposure of osimertinib compared to administration of osimertinib alone. Decreased osimertinib exposure may lead to reduced efficacy (Tagrisso Prescribing Information 2017).

Once enrolled, all patients must try to avoid concomitant use of medications, herbal supplements, and/or ingestion of foods that are known to be potent inducers of CYP3A4 whenever feasible, but patients may receive any medication that is clinically indicated for treatment of AEs. Such drugs must have been discontinued for an appropriate period before a patient enters screening and for a period of 3 months after the last dose of osimertinib. All concomitant medications should be captured on the eCRF. Guidance on medicines to avoid, medications that require close monitoring, and on washout periods is provided in Appendix 4.

